
## Protocol: Glial Regulators for Testing Comorbid Posttraumatic Stress Disorder and Substance Use Disorders

regressed against the parameter estimate obtained from the center voxel from each cluster that exhibited a significant task x seed interaction with the AMY at rest and in response to the alcohol/drug cues (Hypothesis 3A). Changes in CAPS-5 total scores will be regressed against the parameter estimate obtained from the center voxel from each cluster that exhibited a significant task x seed interaction with the AMY at rest and in response to the trauma cue (Hypothesis 3B). Further exploratory analyses will examine change in PFC-AMY connectivity from pre- to post-treatment and associations with other alcohol/drug and PTSD outcomes, both within and between medication groups.

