## Protocol: Glial Regulators for Testing Comorbid Posttraumatic Stress Disorder and Substance Use Disorders

total number of standard drinks consumed and the OCDS total score as the primary outcomes. A Poisson distribution will be assumed with a logarithm link function to assess the effects of NAC treatment. Data collected in substance abuse studies often contain a preponderance of zeros, and these zeros in the distribution can be considered sampling zeros in the Poisson process (Bandyopadhyay et al., 2011). If this excess is present in the distribution, two-part Hurdle models (Poisson and NB) will be explored (Cragg et al., 1971). The hurdle part of the model will allow us to estimate the probability of abstinence during the study period (as an odds ratio) while the Poisson/NB portion will allow for the assessment of the risk of an increase in using days beyond zero during the study period (as a risk ratio). Baseline alcohol/substance use and craving will be included in pertinent models as covariates. Additional alcohol/substance use outcomes will be assessed: change in percent drinking days, percent heavy drinking days, EtG, and VAS craving levels.

Hypothesis 2: NAC treatment will result in significantly greater reduction in PTSD severity (CAPS-5) as compared to placebo. To test this hypothesis, generalized linear mixed effects regression models with a Gaussian distribution will be developed to assess group differences while adjusting for baseline CAPS-5 scores. Assumptions of residual normality and homoscedasticity will be checked using statistical test and graphical methods (Residual and Q-Q plots, and Shapiro-Wilk tests) and transformation will be done as necessary. Restricted maximum likelihood methods will be used to estimate the fixed effects and variance components. Additional outcomes (e.g., PCL-5, CAPS-5 symptom subscales) will be examined.

Hypothesis 3A: Prefrontal cortex-amygdala connectivity at rest and in response to alcohol/drug vs. neutral cues will predict reduction in alcohol/substance use severity (total standard drinks).

Hypothesis 3B: Prefrontal cortex-amygdala connectivity at rest and in response to trauma vs. neutral cues will predict reduction in PTSD severity (CAPS-5).

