For hypotheses 3A and 3B, the following preprocessing and analytical parameters will be used. Preprocessing: Post-acquisition preprocessing and statistical analysis of imaging data will be performed using FEAT (FMRI Expert Analysis Tool) Version 5.98, part of FSL (FMRIB's Software Library). Data will be preprocessed using scripting tools from FEAT. Non-brain signal will be removed using FSL's BET brain extraction. Scans will be corrected for motion using FSL's linear registration and scans will be spatially smoothed. Participants with head motion  $\geq 0.2$  mm will be excluded from the analyses (Power et al., 2012). Motion artifacts will be identified and scrubbed from each subject's data. Scans will be spatially co-registered with a standardized anatomical template (Montreal Neurological Institute) using a 12 parameter affine transformation. Analysis: Functional connectivity will be measured using a psychophysiological interaction (PPI) seed-based approach (Friston et al., 1997). PPI analysis is used to assess the functional coupling between different brain regions. The PPI is defined as the change in connectivity of one area (i.e., the seed region) to another in relation to the experimental context (e.g., alcohol vs. neutral cues). PPI analyses for resting state, trauma and alcohol/drug cues will be performed separately. Customized sq. wave forms representing the trauma run (1=trauma block and -1=neutral block) and the alcohol/drug cue run (1=alcohol/drug block and -1=neutral block) will be convolved with a double-gamma hemodynamic response function. A mask of the seed region will be made using a 12-mm diameter sphere located in the center of the AMY using the MNI coordinates (x, y, z =  $\pm 22, 0, -22$ ). The transformation parameters described above will also be applied to the mask. For each subject, the mean corrected and high pass filtered time series of the BOLD signal in the AMY will be extracted and used in a single subject whole brain PPI analysis. The PPI model will include the task vector, time series of the BOLD signal in the AMY, a term representing the positive task x seed interaction, and a term representing the negative task x seed interaction. The first level analysis will generate contrast images of the parameter estimates for each of the four regressors. Voxels will be thresholded at  $Z > 2.3$  using a corrected cluster threshold of  $p=0.05$ . The contrast images of the parameter estimates of the positive and negative task x seed interactions will be combined for group-level t-tests to identify regions that exhibited altered connectivity with the AMY during the trauma and alcohol/drug cues as compared to neutral cues. All group-level results will be thresholded at  $Z > 2.3$  using a corrected cluster threshold of  $p=0.05$ . Separate linear regression tests will be used to test for associations between PFC-AMY connectivity at baseline and improvement in AUD/SUD and PTSD symptoms during treatment. Changes in total standard drinks will be

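### Hypotheses 3A and 3B are each tested by one regression per significant cluster, with no multiplicity control and no rule for when the hypothesis counts as supported

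*Combined protocol and SAP*

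**What the plan says.** The hypotheses are listed under Statistical Analyses. 3A concerns reduction in total standard drinks. 3B reads "Prefrontal cortex-amygdala connectivity at rest and in response to trauma vs. neutral cues will predict reduction in PTSD severity (CAPS-5"). The analysis text that follows says "Separate linear regression tests will be used to test for associations between PFC-AMY connectivity at baseline and improvement in AUD/SUD and PTSD symptoms". The predictor in each regression is the "parameter estimate obtained from the center voxel from each cluster that exhibited a significant task x seed interaction with the AMY". For 3A the clusters come from the resting map and the alcohol/drug-cue map; for 3B they come from the resting map and the trauma-cue map.

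The amygdala time series is "extracted and used in a single subject whole brain PPI analysis". No prefrontal mask is stated for the cluster search. The only correction given is at map level: "All group-level results will be thresholded at" Z > 2.3 with a corrected cluster p of 0.05. The text gives no significance level for the regressions, no adjustment across clusters or maps, and no statement of what pattern of results would support 3A or 3B. The plan calls exploratory only the analyses that come after these regressions (pre-to-post change in connectivity and associations with other outcomes).

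**The concern.** Each of 3A and 3B makes one claim, that connectivity predicts improvement, but the plan tests it with a number of regressions that is unknown until the maps have been thresholded. More clusters mean more chances of a p-value below .05. The map-level threshold controls false clusters in the search for a group-mean interaction. It says nothing about false associations between a cluster's value and a participant's outcome change, which is a different test on a different variable.

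Hypothesis 3 is one of three numbered hypotheses and has its own power statement, so these regressions are presented as hypothesis tests. Without a decision rule, a reader of the final report cannot tell what error rate lies behind a statement that connectivity predicted response. A chance predictor from about 40 scans could be carried forward as a finding.

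**Working it through.** **The plan's nearest figure.** Power and Sample Size Estimation gives N = 34 for .80 power at effect size 1.0, two-tailed α = .05, citing a study in which connectivity predicted relapse. A two-sample t-test with 17 per group and d = 1.0 has power .807, so the figure reproduces. It is the power of one test, with no allowance for multiplicity.

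**Inputs.**
- n = 40 (Neuroimaging Component), before motion exclusions and dropout.
- Two-sided .05 per regression. This is taken from the power statement, as the regression text gives no level.
- Two maps per hypothesis (rest and cue).
- Clusters per map, c: not in the documents. Assumed 1, 2 or 4.
- Correlation between cluster values: not in the documents. Assumed 0, 0.3 or 0.6.
- Decision rule: not in the documents. Any one p < .05 is assumed to count as support.

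**Independent clusters.** With 2c tests per hypothesis, the chance of at least one p < .05 under no association is 1 − .95^(2c). For 3A or 3B together it is 1 − .95^(4c).
- c = 1: 1 − .95² = 9.8%; 1 − .95⁴ = 18.5%
- c = 2: 1 − .95⁴ = 18.5%; 1 − .95⁸ = 33.7%
- c = 4: 1 − .95⁸ = 33.7%; 1 − .95¹⁶ = 56.0%

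**Correlated clusters.** Simulation with 40,000 replicates: n = 40, 2c normal predictors with a common correlation, outcome independent of all of them, simple regressions. The combined column is 1 − (1 − p)², where p is the per-hypothesis rate, and so treats 3A and 3B as independent.

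| Clusters per map | Correlation | Per hypothesis | 3A or 3B |
|---|---|---|---|
| 1 | 0.3 | 9.5% | 18.1% |
| 1 | 0.6 | 8.7% | 16.6% |
| 2 | 0.3 | 17.3% | 31.6% |
| 2 | 0.6 | 14.6% | 27.1% |
| 4 | 0.3 | 30.2% | 51.3% |
| 4 | 0.6 | 22.6% | 40.1% |

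**Other readings of the plan, four clusters per map, independent tests.**
- Only the cue maps yield clusters: 1 − .95⁴ = 18.5% per hypothesis; 1 − .95⁸ = 33.7% for either.
- A hit is required both at rest and under cue: (1 − .95⁴)² = 3.4% per hypothesis; 1 − (1 − .034)² = 6.8% for either. With correlation 0.6 the per-hypothesis figure rises to 6.8%.

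**The case against.** The strongest reply is that the error rate depends on a rule the plan does not state. 3A and 3B speak of connectivity at rest and under cues. If that means both are required, the chance of false support per hypothesis is close to or below 5% even at four clusters per map. The documents do not exclude that reading, but they do not adopt it either. The missing rule is part of the defect.

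Second, the hypotheses concern prefrontal–amygdala connectivity, so clusters elsewhere in the brain arguably do not test them. In addition, a task-by-seed interaction at rest is undefined because rest has no task, so the resting map may contribute nothing. Both points reduce the count. They stand, and they are why the rates are given as a conditional range.

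Third, the imaging measures are not among the primary clinical outcomes under Assessment Instruments, and the imaging is presented as a guide to later treatment development. That limits the importance of the point. It does not make these regressions exploratory.

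A reader might infer that left and right amygdala seeds double the number of tests, because the seed coordinates are given as ±22. The text describes one mask, one amygdala time series and a four-term model, which reads most naturally as one seed. A reader might also suspect circular selection. However, clusters are chosen on group-mean connectivity and not on outcome, so the inflation shown here comes only from the number of tests.

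**Conclusion.** The point holds in a conditional form. The plan sets no multiplicity control and no decision rule for a data-dependent number of regressions per hypothesis, and the map-level threshold does not supply one. If any one p < .05 counts as support, false support exceeds the nominal 5% already at one cluster per map (about 9–10% per hypothesis). It reaches about 23–34% at four clusters per map for correlations of 0 to 0.6.

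A reader might infer that Hypothesis 3 would be supported by chance about half the time. The documents do not establish that. It would need about four weakly correlated clusters on each of the four map–outcome pairs, pooling of 3A with 3B, and the any-one rule. For either hypothesis alone, the figure stays at about a third or below over the range examined.

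The treatment comparisons under Hypotheses 1 and 2 are unaffected. The change should be made, but it concerns only the imaging predictor claims.

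**What to change.** In the regression text for 3A and 3B:

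- Limit the regressions to prefrontal clusters, and define the resting-state predictor, since a task-by-seed term does not exist at rest.
- State one decision per hypothesis at two-sided .05. Treat all rest and cue regressions for that hypothesis as one family. Declare it supported only if the smallest p-value passes a max-statistic permutation correction, permuting outcome change (or its residuals after the planned covariates) so that the correlation between clusters is kept. Holm's method is simpler.
- Report uncorrected per-cluster slopes as descriptive only.

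A simpler alternative is one pre-specified prefrontal–amygdala measure per map. That gives two tests per hypothesis, with Holm.

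The change needs SAP wording and a short script, and no new data. The cost is power. The plan's d = 1.0 corresponds to r = d/√(d² + 4) = 1/√5 ≈ .45. At n = 40, simulated power for a single cluster is about .84 at α = .05. At a Bonferroni-level threshold it is about .76 with 2 tests (.025), .67 with 4 (.0125) and .58 with 8 (.00625). A fixed-predictor formula gives values about .03 higher (.87, .79, .70 and .61). The loss is somewhat smaller under permutation when clusters are correlated, and larger if motion exclusions or dropout bring n below 40.

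Each hypothesis is then held at .05, so Hypothesis 3 overall stays near 1 − .95² = 9.8% unless 3A and 3B are pooled into one family. The plan should say which is intended.
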